7.2.2. Sample size re-estimation

As appropriate, the sample size of the study may be adjusted using the method outlined by [Cui et al \(1999\)](#). Specific details regarding the method are described in [Appendix 3](#).

9. APPENDICES

Appendix 1. Immune-Related Adverse Events

The MedDRA PTs and clusters for irAEs are defined in the Safety Review Plan (SRP) for avelumab.

Immune-related AEs (irAEs) will be programmatically identified as outlined in Table 16. This case definition is hierarchical, ie, each step is only checked for patients and events that have already met the prior step.

Table 16. Case Definition for irAEs

Step	Selection Criteria	Additional Notes
1	Event selected based on a list of pre-specified MedDRA PTs within clusters. These are included in the SRP as Tier1 events (Immune-mediated xxxx). If AE matches the list, then it is in for the next step	
2	AE onset during 1 st study drug administration or anytime thereafter through 90 days after last dose of study treatment.	This is regardless of start of new anti-cancer drug therapy and regardless of TEAE classifications
3	Answer in the AEECRF page to 'Was another treatment given because of the occurrence of the event' is 'YES'	
4	AE treated with corticosteroids or other immunosuppressant therapy. For endocrinopathies only: AE required hormone replacement	Look in the conmed pages for AE identifiers that match the AEs from Step 3. For each of such AEs if A) OR B) OR C) below are met then the AE is in for the next step A) conmed ATC code is in (H02A, H02B, D07, A01AC, S01BA, S01BB, L04AA, L04AB, L04AC, L04AD, L04AX, A07EA) and AEPT is in any of the irAE clusters. B) conmed ATC code is in (H03A, H03B) and AEPT is in one of the irAE clusters associated with "Immune-mediated endocrinopathies" C) conmed ATC code is A10A and AEPT is in the irAE cluster associated with "Immune-mediated endocrinopathies: Type I Diabetes Mellitus"

5	
A) No clear etiology (other than immune mediated etiology)
 
B) Histopathology/biopsy consistent with immune-mediated event
 
Event is in if [Answer to 5B1 and 5B2 is YES (regardless of answer to 5A)] OR [Answer to 5B1 is YES AND answer to 5B2 is NO AND answer to 5A is NO] OR [Answer to 5B1 is NO AND answer to 5A is NO]
	
A) From the AEECRF page. Is the AE clearly related to an etiology other than immune-mediated etiology? Yes / No If answer is Yes, check all that apply:
 
 • Underlying malignancy/ progressive disease. • Other medical conditions. • Prior or concomitant medications / procedures. • Other. Specify. 
B) From the AEECRF page. B1) Was there a pathology/histology evaluation performed to investigate the AE? Y/N B2) If answer to the above is Yes, does the pathology/histology evaluation confirms an immune mediated mechanism for the AE? Y/N B3) If pathology/histology evaluation performed to investigate the AE, provide summary of relevant findings of the pathology/histology report. (Free Text)

---	---	---

The data set associated with irAEs may be refined based on medical review. The final data set including any changes based on medical review (eg, addition of cases that are not selected by the programmatic algorithm) will be the basis of the irAE analyses.

Appendix 2. Infusion Related Reactions

For defining an AE as IRR, the onset of the event in relation to the infusion of study drug and time to resolution of the event will be considered.

- All AEs identified by the MedDRA PT query describing signs and symptoms will be considered potential IRRs when onset is on the day of study drug infusion (during or after infusion) and the event resolved with end date within 2 days after onset.
- All AEs identified by the MedDRA PTs of Infusion related reaction, Drug hypersensitivity, Anaphylactic reaction, Hypersensitivity, Type 1 hypersensitivity, will be considered potential IRRs when onset is on the day of study drug infusion (during or after the infusion) or the day after the study drug infusion (irrespective of resolution date).

The list of MedDRA PTs for ‘IRRs SIGNS and SYMPTOMS’ and PTs ‘IRRs CORE’ are defined in the SRP for avelumab.

Infusion-related reactions (IRRs) will be programmatically identified as outlined in Table 17 and will be identified for IV drugs only.

Table 17. Case Definition for IRRs – IV Study Drugs Administered Alone Or In Combination With Non-IV Study Drugs

Condition	Selection criterion
If AE meets [1 AND 2] OR [3 AND (4A OR 4B)] then AE is classified as an IRR	
1	PT is included in the ‘IRRs SIGNS and SYMPTOMS’ list
2	
 • AE onset date = date of infusion of study drug AND • AE timing related to study drug (‘DURING’, ‘AFTER’) AND • AE outcome in (‘RECOVERED/RESOLVED’, ‘RECOVERED/RESOLVED WITH SEQUELAE’, ‘RECOVERING/RESOLVING’) AND • AE end date – AE onset date <=2
3	PT is included in the ‘IRRs CORE’ list
4A	
 • AE onset date = date of infusion of study drug AND • AE timing related to study drug in (‘DURING’, ‘AFTER’)
4B	AE onset on the day after infusion

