5.4.3.2. Management of Avelumab Infusion-Related Reactions/Hypersensitivity Reactions

Since avelumab is administered IV, infusion-related reactions may occur (with symptoms such as fever, chills, rigors, diaphoresis, and headache). Treatment of the infusion-related reaction and modifications of avelumab infusion are mainly dependent upon severity, as indicated in Table 4.

Table 4. Treatment Modification for Symptoms of Avelumab Infusion-Related Reactions

| NCI CTCAE Grade | Treatment Modification for Avelumab |
|--|--|
| Grade 1 – mild 
Mild transient reaction; infusion interruption not indicated; intervention not indicated. | 
Decrease the avelumab infusion rate by 50%* and monitor closely for any worsening. |
| Grade 2 – moderate 
Therapy or infusion interruption indicated but responds promptly to symptomatic treatment (eg, antihistamines, NSAIDs, narcotics, IV fluids); prophylactic medications indicated for ≤ 24 hours. | 
Temporarily discontinue avelumab infusion.Resume infusion at 50% of previous rate* once infusion-related reaction has resolved or decreased to at least Grade 1 in severity. Monitor closely for any recurrence or worsening. |
| Grade 3 or Grade 4 – severe or life-threatening 
Grade 3: Prolonged (eg, not rapidly responsive to symptomatic medication and/or brief interruption of infusion); recurrence of symptoms following initial improvement; hospitalization indicated for clinical sequelae. | 
Stop the avelumab infusion immediately and disconnect infusion bag and tubing from the patient.Subjects have to be withdrawn immediately from avelumab treatment and must not receive any further avelumab treatment. |

Table 4. Treatment Modification for Symptoms of Avelumab Infusion-Related Reactions

| NCI CTCAE Grade | Treatment Modification for Avelumab |
|--|-------------------------------------|
| 
Grade 4: Life-threatening consequences; urgent intervention indicated. | |

IV=intravenous, NCI-CTCAE=National Cancer Institute Common Terminology Criteria for Adverse Events, NSAIDs=nonsteroidal anti-inflammatory drugs.

[figure not shown]

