6.6.4. Other significant adverse events

The frequency (number and percentage) of patients with each of the following will be presented for irAEs, by treatment arm:

- irAEs leading to death, by Cluster and PT
- irAEs, by Cluster and PT
- irAEs, Grade ≥ 3 , by Cluster and PT
- irAEs leading to discontinuation of avelumab, by Cluster and PT
- irAEs leading to discontinuation of BSC, by Cluster and PT
- Serious irAEs, by Cluster and PT

The listing of all irAEs will also be provided with the relevant information with a flag for irAEs with onset outside of the on-treatment period.

The frequency (number and percentage) of patients with each of the following will be presented for IRRs, by treatment arm:

- IRRs leading to death, by PT
- IRRs, by PT
- IRRs, Grade ≥ 3 , by PT
- IRRs leading to discontinuation of avelumab, by PT
- Serious IRRs, by PT
- Time related to first onset of an IRR (infusion 1, infusion 2, infusion 3, infusion 4 or later).

The listing of all IRRs will also be provided with the relevant information with a flag for IRRs with onset outside of the on-treatment period.

In addition, the following analyses will be presented for irAEs (as defined in [Appendix 1](#)) and Tier-2 events separately. CIs for risk difference will be calculated based on the unconditional exact method by [Santner and Snell \(1980\)](#). No additional analyses will be presented for Tier-3 AEs.

- Frequency (number and percentage) of patients with each of the following by treatment arm and PT or Clustered Term:
 - Tier-2 AEs
 - Tier-2 AEs Grade ≥ 3
- Point estimate for risk difference and 95% CI for risk difference (experimental arm vs comparator arm) for each of the following by PT or Clustered Term:
 - irAEs
 - irAEs Grade ≥ 3
 - Tier-2 AEs
 - Tier-2 AEs Grade ≥ 3
- CIs reported are not adjusted for multiplicity and should be used for screening purposes only. The 95% CIs are provided to help gauge the precision of the estimates for the risk difference and should be used for estimation purposes only.

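### Infusion reactions reported only as symptoms cannot enter the fatal, Grade ≥3 or serious IRR tables if they are fatal, not recovered, longer than 2 days or without an end date

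*SAP*

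**What the plan says.** SAP Appendix 2 gives two routes to an IRR. Table 17 joins them as follows: "If AE meets [1 AND 2] OR [3 AND (4A OR 4B)] then AE is classified as an IRR".

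- **Signs-and-symptoms route (conditions 1 and 2).** The text requires onset on the infusion day ("during or after infusion) and the event resolved with end date within 2 days after onset"). Table 17 turns this into four tests that must all be met: onset date equal to the infusion date; timing DURING or AFTER; an outcome of RECOVERED/RESOLVED, "RECOVERED/RESOLVED WITH SEQUELAE’, ‘RECOVERING/RESOLVING"; and "AE end date – AE onset date <=2".
- **Core route (conditions 3 and 4A or 4B).** This covers the "MedDRA PTs of Infusion related reaction, Drug hypersensitivity, Anaphylactic reaction, Hypersensitivity, Type 1 hypersensitivity" terms. They count with onset on the infusion day (during or after) "or the day after the study drug infusion (irrespective of resolution date"). There is no outcome test and no duration test.

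SAP 6.6.4 then tabulates "IRRs leading to death, by PT", along with Grade ≥3 and serious IRRs, from both routes together. SAP 6.6.1 defines an event leading to death by a fatal outcome or Grade 5. The two term lists are held in the Safety Review Plan. Appendix 1, on immune-related events, lets medical review add cases that the program misses. Appendix 2 has no such provision.

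**The concern.** On the signs-and-symptoms route, whether an event is a case depends on how it ended, and the cases are then tabulated by how they ended. A fatal outcome is not among the allowed outcomes, so this route can contribute no such event to the fatal-IRR table. Its contribution to the Grade ≥3 and serious tables can also be too low.

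The route is not a formality. Protocol 5.4.3.1 describes infusion reactions through individual symptoms such as dyspnea, hypotension and wheezing, and a site may report those rather than a diagnosis. Protocol Table 4 characterizes a Grade 3 reaction partly as "Prolonged (eg, not rapidly responsive to symptomatic medication and/or brief interruption of infusion"), so the filter runs in the same direction as severity.

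IRRs are adverse events of special interest in SAP 3.5.1 and an important risk in Protocol 1.3. The same classification feeds the safety comparison by anti-drug-antibody status in SAP 6.2.6.3. Severe IRRs are expected to be few, so one misclassified event would be visible in these tables.

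**Working it through.** **1. The rule applied case by case.** Inputs are the four tests of Table 17 condition 2 and conditions 4A and 4B. For a signs-and-symptoms term with infusion-day onset and timing DURING or AFTER:

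| Outcome | Ends 0–2 days after onset | Ends 3 or more days after onset | No end date |
|---|---|---|---|
| Recovered | IRR | not IRR | not IRR |
| Recovered with sequelae | IRR | not IRR | not IRR |
| Recovering | IRR | not IRR | not IRR |
| Not recovered | not IRR | not IRR | not IRR |
| Fatal | not IRR | not IRR | not IRR |

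For a core term with infusion-day or next-day onset, every cell is an IRR. Grade and seriousness appear nowhere in condition 2, so a severe or serious symptom with an allowed outcome that ends within 2 days is kept.

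**2. Missing end dates.** SAP 5.3.2.2 imputes a stop date only when the day alone is missing, using month-end or the date of death if that is earlier. Otherwise the stop date stays incomplete. Two things follow. A recovering event with no end date fails the end-date test, although its outcome is on the allowed list. A short event whose stop day is missing can be moved past 2 days by the month-end rule.

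**3. Text against table.** The text requires a resolved event. Table 17 admits a recovering one, provided it has an end date. The two do not describe the same rule.

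**4. What the protocol's earlier cohort shows (Protocol 1.2.2.1, 717 patients).** The IRR counts agree internally: by grade, 30 + 101 + 5 + 2 = 138; by infusion of onset, 91 + 35 + 9 + 3 = 138; and 138/717 = 19.2%.

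- Grade 3–4 IRRs: 5 + 2 = 7, and 7/717 = 0.98%.
- Protocol Table 2 lists 7 patients with a Grade ≥3 event under the core term Infusion related reaction, which is the same count.
- Protocol Table 1 lists 134 patients at any grade under that term. The difference is 138 − 134 = 4, and 4/138 = 2.9%.

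If the seven are the same patients, 0 of 7 severe reactions were coded outside the core term. The one-sided 95% upper limit for that share is 1 − 0.05^(1/7) = 34.8%. It bounds only the share coded as symptoms, not the share that would also fail the outcome or end-date test.

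**5. Size in this trial.** A figure would need the share of severe IRRs reported only as symptoms, and the share of those that are fatal, not recovered, longer than 2 days or without an end date. The documents give neither.

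**The case against.** The strongest reply is that the filter is deliberate and its reach is narrow. Fever, dyspnea, hypotension and back pain are nonspecific in patients with advanced cancer who are infused every 2 weeks, and a short time limit protects specificity. The core terms, which include anaphylaxis, count whatever their outcome or duration. Excluded treatment-emergent events still appear in the tables by term and worst grade and in the fatal-event tables (SAP 6.6.1.1), among discontinuations (6.6.1.4), in the death listing (6.6.2) and among serious events (6.6.3). All of this stands. What is lost is the IRR label in a descriptive table, and no efficacy conclusion depends on it.

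Two stronger readings are tempting and should be resisted.

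- A reader might infer that the IRR tables lose the worst reactions in general. The core route and the retained short severe symptoms rule that out. Nor does Protocol Table 4 support it: its word for prolonged is explained by poor response to medication or to a brief interruption, with no 3-day threshold.
- A reader might scale 7/717 to 0.0098 × 334 = 3.3 severe IRRs in Arm A (assuming 668/2 = 334 patients, all treated) and suppose that one or two would drop out. Nothing in the documents supports that supposition, and the match of 7 with 7 points the other way.

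The match does not clear the rule either. Protocol Table 2 counts treatment-related events, equal counts need not be the same patients, and the IRR definition behind the 138 is not stated. If that definition used a similar filter, prolonged symptoms would be missing from the 138 as well. The cohort also had no Grade 5 IRR, so the expected number of fatal cases is small.

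**Conclusion.** The point holds for reactions reported only as signs or symptoms. Such an event, if fatal, not recovered, longer than 2 days or without an end date, cannot be counted as an IRR, and Appendix 2 states no review step to recover it. For Outcome = Fatal the exclusion is complete by definition. For Grade ≥3 and serious IRRs the effect can only lower the counts, by an amount that cannot be computed without the Safety Review Plan lists and the coding practice; it may be zero.

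This rests on Table 17 being programmed as written and on no core term being reported for the same reaction. It concerns descriptive safety tables for an important risk. It is worth correcting because the case definition depends on the outcome being tabulated and the correction is cheap.

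**What to change.** - Keep the current algorithm for the main IRR table.
- For the fatal, Grade ≥3 and serious IRR tables in SAP 6.6.4, add a supplementary count that drops the outcome and end-date tests for signs-and-symptoms terms with infusion-day onset (DURING or AFTER) that are Grade ≥3, serious, fatal or led to avelumab withdrawal.
- Flag the added cases in the IRR listing and make them subject to a medical-review step like the one in Appendix 1.
- Reconcile the Appendix 2 text, which requires resolution, with the RECOVERING/RESOLVING outcome in Table 17. Either remove that outcome or state how it is handled when there is no end date.

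The cost is a short SAP edit and a small programming change. The downside is that a few severe same-day events of other cause may be counted in the supplementary table. The flag and the medical review contain this, and the main table is unchanged.

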Appendix 3. Technical Details For Sample Size Re-Estimation

In 1999, Cui et al published the form of the test statistic at the final analysis if a sample size adjustment is performed in an adaptive design with normal endpoints. Using the proposed weighted test statistic ensures that the overall Type 1 error is maintained at the pre-specified level.

In 2007, Mehta presented an extension of Cui’s method to time to event (TTE) endpoints reported using the two-sample log-rank test (LRT). This extension is based on results published in 1981 by Tsiatis (1981) who showed that the sequentially computed scores

statistics of the proportional hazards model converges asymptotically to a multivariate normal process with independent increments. Cui's method for normal endpoints is applied to the LRT, as a special case for the efficient scores test for the proportional hazards model.

The proposed weighted LRT statistic (T_2) calculated at the final analysis after a sample size increase preserves the Type 1 error.

$$T_2 = \sqrt{t_1} Z_1 + \sqrt{1 - t_1} \left(\frac{\sqrt{t_2^*} Z_2^* - \sqrt{t_1} Z_1}{\sqrt{t_2^* - t_1}} \right) \quad (1)$$

where:

t_1 = Information fraction at the interim analysis

t_2^* = Information fraction for LRT statistic at the final analysis after a sample size increase

Z_1 = LRT statistic at interim analysis

Z_2^* = LRT statistic at final analysis after a sample size increase.

In 1992, Kim showed that the sequentially computed stratified log-rank test (SLRT) statistics has an asymptotic multivariate normal distribution with independent increments. Based on this result and using a similar approach as presented by Mehta, Cui's method can be further extended to TTE endpoints reported using the SLRT. Similarly, the proposed weighted SRLT statistic (U_2) calculated at the final analysis after a sample size increase preserves the Type 1 error.

$$U_2 = \sqrt{u_1} S_1 + \sqrt{1 - u_1} \left(\frac{\sqrt{u_2^*} S_2^* - \sqrt{u_1} S_1}{\sqrt{u_2^* - u_1}} \right) \quad (2)$$

where:

$u_1 = D_1/D_{max}$ = Information fraction at the interim analysis; D_1 = total number of events at the time of interim analysis and $D_{max} = 200$

u_2^* = Information fraction at the final analysis after a sample size increase

S_1 = LRT, at interim analysis, stratified for baseline stratification factors

S_2^* = LRT, at final analysis after a sample size increase, stratified for baseline stratification factors

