1.2.3.3. Rationale for Study Design

As described in the previous section, recent data demonstrate that immune checkpoint inhibitors, including avelumab, are capable of inducing objective tumor response in advanced UC patients and may provide further clinical benefit by prolonging overall survival.^{41,42,51,55}

The strategy of the proposed trial is to maintain or extend early clinical benefit following completion of first-line platinum-based chemotherapy in patients with advanced urothelial cancer by providing maintenance immunotherapy with avelumab. In this study, patients assigned to receive avelumab may continue to do so until their disease progresses or they discontinue due to other reasons. The potential benefits of avelumab maintenance therapy may include delay in the subsequent treatment with more toxic 2nd line chemotherapy as well as an improvement in overall survival.

An open-label design was chosen over a double-blind placebo-controlled design after assessment of risk-benefit considerations. As the study medication (avelumab) is administered as a 1-hour infusion, the use of an intravenous placebo would be associated with some risks (eg, injection site reactions) and with no benefit to the patient. Additionally, in order to preserve the blind, the use of a placebo infusion would require premedication with an H1 blocker and paracetamol prior to infusion as required for patients receiving avelumab to limit the incidence and severity of infusion-related reactions, an unnecessary practice for patients receiving placebo.

Overall survival (OS) will be the primary endpoint. PFS assessed by Blinded Independent Central Review (BICR) as well as the objective response as determined by RECIST v1.1 guidelines, will be secondary endpoints.

At the pre-specified interim analysis ([Section 9.6](#)), this study met the primary objective and demonstrated that avelumab plus BSC significantly prolongs OS compared to BSC alone in both co-primary populations (ie, in all randomized patients and in patients with PD-L1-positive tumors). Based on this result, the E-DMC recommended that remaining patients on Arm B who are progression-free be offered crossover to avelumab. For additional information, please refer to Supplement 1.

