5.1.2. Decision rules

To protect the integrity of the study and to preserve the type I error rate, a fraction of alpha for efficacy will be spent at the interim analysis and accounted for in the overall type I error rate (if the interim analysis is performed exactly at the planned number of OS events, alpha spent at interim is 0.005 for all patients and 0.002 for patients with PD-L1-positive tumors). The significance levels for the interim and final efficacy analyses of OS will be determined by using the Lan-DeMets procedure with an O'Brien-Fleming stopping boundary. The overall significance level for the efficacy analysis of OS will be preserved at (one-sided) 0.015 for all patients and 0.01 for patients with PD-L1-positive tumors.

Two analyses will be performed for OS:

The interim analysis of OS will be performed after at least 315 of all randomized patients have died (74% of the target number of OS events for the 'all patients' population), and all of the following conditions have been met:

- 1) all initially planned patients have been randomized, and
- 2) at least 146 patients with PD-L1-positive tumors have died (approximately 66.7% of the total OS events expected in the 'patients with PD-L1-positive tumors' population).

The primary analysis of OS will be performed after at least 425 of all randomized patients and at least 219 patients with PD-L1-positive tumors have died, and the last patient randomized in the study has been followed for at least 12 months after randomization.

The study will have met its primary objective if the experimental arm is statistically significantly superior to the control arm for either one of the co-primary populations, either at the time of the interim analysis or at the time of the final analysis.

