7.2.1. Interim analysis for OS

Let $u(t_1)$ and $u(t_F)$ denote the upper critical boundaries based on the test statistics Z_1 and Z_F for efficacy at the interim and the final analysis, respectively, and let $l(t_1)$ and $l(t_F)$ denote the lower critical boundary for futility at the interim and final analysis, respectively. For the final analysis, $l(t_F)=u(t_F)$.

The critical values $u(t_1)$ and $l(t_1)$ for the interim analysis of OS are determined such as

$$P_0(Z_1 \geq u(t_1)) = \alpha(t_1) \quad \text{and} \quad P_a(Z_1 \leq l(t_1)) = \beta(t_1) ,$$

where P_0 and P_a denote the probabilities under the null hypothesis and the alternative hypothesis, respectively, and $\alpha(t_1)$ and $\beta(t_1)$ denote the α and β spent, respectively, based on

the predefined spending functions at information fraction t_1 (t_1 is calculated as the ratio of the number of OS events observed at the time of the cut-off for the interim analysis and the total number of OS events targeted for the final analysis).

The boundary for the final efficacy analysis will be calculated such that

$$\alpha(t_1) + P_0(Z_1 < u(t_1), Z_F \geq u_F) = \tau$$

$\tau=0.015$ for 'all patients' population,

$\tau=0.01$ for 'patients with PD-L1-positive tumors' population

As described in [Section 5.1.2](#), if the number of OS events in the final analysis deviates from the target number of OS events, the final analysis criteria will be determined as above taking into account the actual alpha spent at the interim analysis and the actual correlation between the two test statistics Z_1 and Z_F , so that the overall one-sided significance level across all analyses and comparisons is preserved at 0.025.

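### SAP Appendix 3 fixes Dmax at 200, so the weighted test for an interim sample-size increase cannot be computed for all patients, whose interim needs at least 315 deaths

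*SAP*

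**What the plan says.** SAP 7.2.2 provides that, as appropriate, "the sample size of the study may be adjusted using the method outlined by" a cited 1999 paper on changing the sample size in group-sequential trials, and refers to Appendix 3 for the details. Protocol 9.6 and SAP 5.1.2 list the same option among the possible interim actions.

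Appendix 3 gives two weighted final statistics. T2 is for the unstratified log-rank test and U2 for the stratified one. The primary analysis in SAP 6.1.1.1 is stratified, so U2 is the one that applies:

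U2 = sqrt(u1)·S1 + sqrt(1 - u1)·[sqrt(u2*)·S2* - sqrt(u1)·S1] / sqrt(u2* - u1)

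Here u1 = D1/Dmax. D1 is described as the "total number of events at the time of interim analysis and" Dmax is given the single value 200. The other fraction, u2*, is described only as "Information fraction at the final analysis after a sample size increase", with no denominator.

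Elsewhere the SAP uses different denominators:

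- SAP 7.2.1 divides the OS events observed at the interim by "the total number of OS events targeted for the final analysis".
- SAP 5.1.2 calls 315 all-patient deaths "74% of the target number of OS events" and 146 PD-L1-positive deaths "approximately 66.7% of the total OS events expected".
- SAP 5.1.2 places the primary analysis after "at least 425 of all randomized patients and at least 219 patients with PD-L1-positive tumors have died".

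**The concern.** An information fraction at an interim look must lie between 0 and 1. With a denominator of 200 and an interim that needs at least 315 deaths, it exceeds 1 for all randomized patients, and the second-stage weight becomes the square root of a negative number. A statistic that the plan names for a co-primary population then has no value on a branch that the plan permits.

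The method protects the type 1 error because the stage weights are fixed before the interim data are seen. The written constant is therefore part of what is pre-specified. A single Dmax also cannot serve two populations with different event targets.

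**Working it through.** **Inputs.** Interim minimums of 315 (all patients) and 146 (PD-L1-positive) deaths, from SAP 5.1.2. Final targets of 425 and 219 deaths, with one-sided alpha 0.015 and 0.01, from SAP 5.1.1. Interim efficacy boundaries of 2.595 and 2.947, from SAP Table 5. Dmax = 200, from SAP Appendix 3.

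**1. Which denominators does the design use?** Lan-DeMets O'Brien-Fleming spending at fraction t is 2·[1 - Φ(z(1 - α/2)/sqrt(t))].

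| Population | t | Alpha spent | Interim z | Table 5 | Final z |
|---|---|---|---|---|---|
| All patients | 315/425 = 0.741 | 0.00472 | 2.595 | 2.595 | 2.210 |
| PD-L1-positive | 146/219 = 0.667 | 0.00161 | 2.947 | 2.947 | 2.346 |
| PD-L1-positive, denominator 200 | 146/200 = 0.730 | 0.00257 | 2.798 | 2.947 | – |

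The printed boundaries follow from 425 and 219. Two-look power, ignoring the non-binding futility bound, is 93.1% and 80.2%, against 93% and 80% in the SAP. Nothing in the design rests on 200.

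**2. U2 for all patients with Dmax = 200.** u1 = 315/200 = 1.575 at the earliest permitted interim, and 1 - u1 = -0.575. The weight sqrt(-0.575) is imaginary. More interim deaths make 1 - u1 more negative, so no permitted interim gives a real U2. With Dmax = 425, u1 = 0.741 and the weights are sqrt(0.741) = 0.861 and sqrt(0.259) = 0.509.

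**3. U2 for PD-L1-positive patients with Dmax = 200.** At 146 deaths u1 = 0.73, and the weights are sqrt(0.73) = 0.854 and sqrt(0.27) = 0.520. With Dmax = 219 they are sqrt(0.667) = 0.816 and sqrt(0.333) = 0.577. Keeping the boundaries 2.947 and 2.346 but using correlation sqrt(0.73) between the two stages gives one-sided alpha 0.00986 instead of 0.0100. Above 200 interim deaths, U2 would fail here too.

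**4. The missing denominator of u2\*.** If u2* is the final number of events D2 divided by the same Dmax (425), the all-patients alpha is 0.0150 whatever D2 is. If u2* is read as a fraction of the enlarged total, then u2* = 1, the factors sqrt(1 - u1) and sqrt(u2* - u1) cancel, and U2 reduces to the unweighted S2*. Its correlation with S1 is sqrt(315/D2). Assuming a fixed increase in events and the unchanged boundaries 2.595 and 2.210:

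| Increase | D2 | One-sided alpha |
|---|---|---|
| 10% | 467.5 | 0.0154 |
| 25% | about 531 | 0.0159 |
| 50% | 637.5 | 0.0163 |

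**The case against.** The strongest reply is that the SAP repairs itself. SAP 7.2.1 defines the interim information fraction, Appendix 3 uses the same name for u1, and the targets of 425 and 219 are stated plainly. A statistician who applied the formula to all patients would meet an imaginary number at once and substitute 425. In that population the error cannot silently produce a wrong result, and 200 looks like a leftover constant. The branch is also optional, and Protocol 1.2.3.3 reports that "avelumab plus BSC significantly prolongs OS compared to BSC alone in both co-primary populations" at the interim.

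Much of this stands. It limits the consequence: no reported result depends on U2, and the right value is not open to choice after unblinding. It does not make the written rule correct. Appendix 3 is where SAP 7.2.2 sends the reader, no other section gives a different Dmax for U2, and the branch was available when the SAP was written. Using T2 instead does not help, since T2 is unstratified and the primary test is stratified.

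The objection to the u2* figures also has force. In sqrt(u2* - u1) the two fractions must share a scale, so the same Dmax is the natural reading. The alphas of 0.0154 to 0.0163 belong to the less natural one and assume an increase that does not depend on the interim data. They show why the denominator should be written down, and they do not measure the main error. Likewise, the PD-L1-positive figures hold at the minimum of 146 deaths; the actual interim count could be higher, because the interim waits for the later of the two milestones.

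**Conclusion.** The concern holds. As written, U2 is undefined for all randomized patients at every permitted interim. That conclusion rests only on two numbers in the SAP, 200 and 315, and needs no assumption. For PD-L1-positive patients the effect at 146 deaths is small and conservative. This is an internal contradiction in the pre-specified plan, confined to the optional sample-size branch. It should be corrected, but it does not call into question the group-sequential boundaries, the ordinary stratified log-rank test at 425 and 219 events, or the reported interim result.

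**What to change.** In SAP Appendix 3:

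- Replace the single value 200 by Dmax = 425 for all randomized patients and Dmax = 219 for patients with PD-L1-positive tumors. State that equation (2) is applied separately in each population, with u1 as defined in SAP 7.2.1.
- Define u2* as the number of events at the final analysis after the increase, divided by the same Dmax.

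At the planned interim counts the weights are then 0.861 and 0.509 for all patients, and 0.816 and 0.577 for PD-L1-positive patients. The cost is two lines of SAP wording. Patients, data collection, timing and the ordinary primary test are unchanged.
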